6.3. Lifestyle Restrictions

Subjects must have a stable lifestyle with no changes to dietary or exercise habits during the course of the study.

6.4. Screen Failures

Individuals who do not meet the criteria for participation in this study (screen failure) may be rescreened.

7. Treatments

7.1. Treatments Administered

This study involves the treatment of subjects with diabetes with marketed insulin lispro (100 units/mL) administered by the pen. Table IOQV.3 shows the treatment regimens. Subjects will continue their pre-study concomitant anti-hyperglycemic medication and basal insulin therapies during the study.

Table IOQV.3. Treatment Regimens

Study Period 1	Study Period 2
Insulin lispro doses as prescribed delivered via the pen. CGM data blinded.	Insulin lispro doses as prescribed delivered via the pen. CGM data unblinded.

Abbreviation: CGM = continuous glucose monitoring.

The investigator or his/her designee is responsible for the following:

- explaining the correct use of the pen, the commercially available CGM device, and the glucometer to the subject or the subject's legal representative.
- maintaining accurate records of all pens, medication vouchers/pharmacy cards, and device dispensing and collection.
- at the end of the study, all pens, the CGM device, and glucose meter must be returned to Lilly or its designee.

7.1.1. Packaging and Labeling

Clinical study materials will be labeled according to United States (US) regulatory requirements.

7.1.2. Medical Devices

The medical device provided for use in the study is the investigational reusable insulin injection pen, which collects dose administration information. The other devices provided for use during the study are a commercially available CGM device (CCI [REDACTED]) and a glucose meter.

As each subject completes the study, accountability will be completed and the returned items will be stored as instructed. Detailed information about this process will be available as part of site's working manual.

7.1.2.1. Continuous Glucose Monitoring

The commercially available CGM device that will be used during the study is the CCI [REDACTED], which consists of a glucose sensor, data transmitter, and data receiver that assesses interstitial glucose readings every 5 minutes. The CCI [REDACTED] can be blinded or unblinded. The CCI [REDACTED] should be calibrated at least once every 12 hours by a finger stick blood glucose reading from the provided glucose meter. The calibration of the CCI [REDACTED] should be done during both study periods when the CGM system is in use.

7.1.2.2. Investigational Reusable Insulin Injection Pen

The insulin injection device to be used in Study IOQV is an investigational reusable pen injector for the delivery of a subcutaneous injection of insulin using the standard Lilly 3 mL Humalog U-100 glass cartridges. The pen is a variable dose device for use in patients with T1D or T2D. The pen dials in 1-unit increments with a 60 unit maximum dose, and requires a new pen needle for each injection. The pen contains an organic light-emitting diode display and memory function which allows for insufficient remaining dose detection (while displaying the remaining partial dose), last dose display (time since last dose and units delivered), a full dose history in memory, and “Injection Complete” prompt. The pen contains electronics with the capability to store dosage data and download the data by the study site personnel. Due to the investigational nature of the reusable insulin injection pen, this study is also following 21 CFR 812 guidelines for investigational devices.

7.2. Method of Treatment Assignment

Subjects who meet all inclusion/exclusion criteria (Sections 6.1 and 6.2) will be enrolled into the study at Visit 1 (Week 0). This study is an open-label, single-arm study for which all subjects are receiving insulin lispro 100 units/mL.

7.2.1. Selection and Timing of Doses

The doses will be administered according to the subject’s usual practices. The actual dose and time of all dose administrations will be recorded by the pen and downloaded by study site personnel. Subjects will continue their prestudy basal insulin and concomitant antihyperglycemic therapy and the investigator may make insulin dose adjustments as indicated.

7.3. Blinding

This is an open-label study. Subjects and study personnel will not be blinded to insulin lispro 100 units/mL administered via the pen. Subjects will not have access to their historical bolus dosing data from the pen with the exception of the display indicating the duration since their last bolus dose. Additionally during Study Period 1, subjects will be blinded to their CGM readings (Figure IOQV.1). Subjects and the study personnel will be unblinded to the subject’s CGM data during Study Period 2.

7.4. Dosage Modification

Insulin dosage modifications are not required during the study but may be indicated. Therefore, insulin adjustments are allowed based on the investigator’s medical judgement using the available glucose and insulin data. Subjects who are adjusted to a single bolus insulin dose of >40 units per injection will be discontinued from the study.

7.5. Preparation/Handling/Storage/Accountability

The investigator or his/her designee is responsible for the following:

- Device training on the pen, CGM system, and glucometer.
- Completion of the checklist for all device training.

- Ensuring that only subjects receive study treatment vouchers.
- The investigator, institution, or the head of the medical institution (where applicable) is responsible for study treatment voucher accountability, reconciliation, and record maintenance (such as receipt, reconciliation, and final disposition records).

7.6. Treatment Compliance

Compliance of pen utilization will be assessed at each visit. To avoid missing data, the pen and CGM data will be downloaded at predetermined time points described in the SOA.

7.7. Concomitant Therapy

Other concomitant therapies that are part of routine care are allowed and can be used during the study at the investigator's discretion. A list of medications not allowed will be provided separately. Any change in the list of medications not allowed will be communicated to investigators, and will not constitute a protocol amendment.

A subject's concomitant antihyperglycemic therapy may be adjusted as needed per investigator's discretion for safety.

7.8. Treatment after the End of the Study

7.8.1. Treatment after Study Completion

The pen or insulin lispro will not be made available to study participants after conclusion of the study. Subjects will resume their standard insulin therapy at the completion of the study.

8. Discontinuation Criteria

8.1. Discontinuation from Study Treatment

8.1.1. Permanent Discontinuation from Study Treatment

Discontinuation from study treatment (i.e., the pen) for a total of >3 days would lead to permanent discontinuation from study treatment as the purpose of the study is to collect data on bolus dosing. If a subject is permanently discontinued from study treatment, they will also be discontinued from the study.

8.1.2. Temporary Discontinuation from Study Treatment

Subjects may temporarily discontinue study treatment for a total of ≤ 3 days due to temporary hospitalization, medical procedure, loss of the pen, or per the investigator's judgement.

8.1.3. Discontinuation of Inadvertently Enrolled Subjects

If the sponsor or investigator identifies a subject who did not meet enrollment criteria and was inadvertently enrolled, then the subject should be permanently discontinued from study treatment. Safety follow-up is as outlined in the SOA ([Table IOQV.1](#)), Section 9.2 (Adverse Events), and Section 9.4 (Safety) of the protocol.

8.2. Discontinuation from the Study

Subjects will be discontinued in the following circumstances:

- if the subject becomes pregnant during the study as determined by a serum or urine pregnancy test performed at the investigator's suspicion of possible pregnancy.
- enrollment in any other clinical study involving an investigational product or enrollment in any other type of medical research as judged by the sponsor not to be scientifically or medically compatible with this study.
- for medical, safety, regulatory, or other reasons consistent with applicable laws, regulations, and good clinical practice (GCP).
- subjects who are adjusted to a single bolus insulin dose of >40 units per injection.
- if the subject discontinues study treatment for a total of >3 days.
- **Investigator Decision**
 - the investigator decides that the subject should be discontinued from the study.
 - if the investigator deems it necessary to stop insulin lispro treatment.
- **Subject Decision**

- the subject or the subject's designee requests to be withdrawn from the study.
- **Sponsor Decision**
 - if the subject loses or otherwise renders the pen (and its replacement pen) inoperable, the sponsor may discontinue that subject from the study.
 - the sponsor decides to stop the study.

Subjects discontinuing from the study prematurely for any reason should complete AE and other safety follow-up per Section 2 (SOA), Section 9.2 (Adverse Events), and Section 9.4 (Safety) of this protocol.

8.3. Lost to Follow-Up

A subject will be considered lost to follow-up if he or she repeatedly fails to attend scheduled visits and is unable to be contacted by the study site. Site personnel are expected to make diligent attempts to contact subjects who fail to return for a scheduled visit or were otherwise unable to be followed up by the site.

9. Study Assessments and Procedures

Section 2 lists the SOA, with the study procedures and their timing (including tolerance limits for timing).

9.1. Efficacy Assessments

9.1.1. Primary Efficacy Assessments

The primary efficacy assessment objectively estimates the average number of days per month with a missed bolus dose in subjects with type 1 or type 2 diabetes using blinded CGM measurements and the pen. Missed bolus doses will be determined by the glucose excursion as measured by the CGM.

- A subject is counted as missing 1 injection, if the subject does not have any injection record during the 1-hour interval prior to a glucose excursion (≥ 80 mg/dL) in the 2-hour postprandial interval.

Example: In the theoretical CGM profile (Figure IOQV.2), 2 glucose excursions ≥ 80 mg/dL within a 2-hour interval are observed:

- nadir at 11 am and peak at 12 pm,
- nadir at 1:30 pm and high at 2:15 pm.

If the associated insulin pen data show no injection between 10 am and 11 am and 1 injection between 12:30 pm and 1:30 pm, then the subject has 1 missed injection corresponding to the 11 am-12 pm glucose excursion.

Figure IOQV.2. Example of a missed injection using a CGM profile.

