3.1. Study Rationale

Current diabetes management using basal/bolus insulin regimens requires a high level of patient engagement. One-third of patients with type 1 diabetes (T1D) or type 2 diabetes (T2D) reported insulin omission/nonadherence at least once in the past month. Of those patients, there was an average of 3.3 days per month of insulin omission/nonadherence (Peyrot et al. 2012). Patients often cite being too busy, fear of hypoglycemia, and concerns about weight gain as reasons for missing doses (Peyrot et al. 2012). Downloaded dosage data from insulin pump users indicated that 65% of pump-using children/adolescents with T1D missed 1 or more mealtime insulin bolus doses per week, with an association between missed bolus doses and glycated hemoglobin (HbA1c) results (Burdick et al. 2004). Prior to the development of insulin injection pens that track dose data, missed dosage data for multiple daily injection users was obtained by patient survey results only. The investigational reusable insulin injection pen (hereafter referred to as “pen”) affords the opportunity to objectively gather omitted or suboptimal insulin dose data via pen download. Additionally, the continuous glucose monitoring (CGM) allows an assessment of the impact of bolus dosing on short-term glycemic control.

Study F3Z-MC-IOQV (IOQV) is an exploratory study to objectively estimate the average number of days per month subjects have a missed bolus dose in subjects with T1D or T2D with blinded CGM. In addition, the study will explore any differences in missed bolus insulin doses by diabetes type, by CGM (blinded, unblinded), and by subject characteristics. Study IOQV will utilize data from the pen to obtain bolus dose data (including amount and time of dose), along with blinded and unblinded CGM to assess short-term glycemic control.

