6.2. Exclusion Criteria

Patients will be excluded from study enrollment if they meet any of the following criteria:

Medical Conditions

- [9] Subjects with known tape/adhesive allergies with CGM sensors.
- [10] Subjects with medical conditions, visual, physical, psychiatric, or cognitive impairment(s) that may preclude the ability to participate in the trial per the investigator's discretion.
- [11] Have a documented medical history of or obvious clinical signs or symptoms of liver disease, acute or chronic hepatitis, or a history of alanine aminotransferase or aspartate aminotransferase levels ≥ 3 times the upper limit of the reference range within the last 6 months before screening.
- [12] Have documented medical history of chronic kidney disease stage 4 and higher within the last 6 months before screening or history of renal transplantation.
- [13] Have active malignancy.
- [14] Are pregnant or planning to become pregnant.
- [15] Are on or are intending on beginning a weight loss program.

Prior/Concomitant Therapy

- [16] Subjects with T1D who have taken off-label antihyperglycemic agents within 3 months prior to screening.
- [17] Have received insulin by continuous subcutaneous insulin infusion in the 3 months prior to screening.
- [18] Subjects taking opioid medications at screening for medically invalid reasons or at doses considered excessive for the treated condition per the investigator's discretion.
- [19] Subjects on routine use of acetaminophen at screening per the investigator's judgement.

[20] Currently undergoing systemic treatment with:

- Immunosuppressive medication.
- Chronic (lasting longer than 2 weeks) systemic glucocorticoid therapy (excluding topical and inhaled preparations) or have received such therapy within 2 weeks immediately before Visit 1 (Week 0).

Prior/Concurrent Clinical Trial Experience

[21] Are currently enrolled in any other clinical study involving an investigational product or any other type of medical research judged not to be scientifically or medically compatible with this study.

[22] Have participated, within the last 30 days, in a clinical study involving an investigational product. If the previous investigational product has a long half-life, 5 half-lives or 30 days (whichever is longer) should have passed.

[23] Have previously completed or withdrawn from this study.

Other Exclusions

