9.1.2. Secondary Assessments

Study IOQV will have 5 secondary efficacy measures as described in Table IOQV.2. The first secondary objective is similar to the primary objective (Section 9.1.1) except that the information to be analyzed will be using unblinded CGM data. Missed bolus doses will be determined by the glucose excursion as measured by the unblinded CGM.

Study IOQV will also estimate the percent time-in-range in subjects with T1D or T2D using blinded and unblinded CGM data. The glucose range for this analysis is >70 and ≤ 180 mg/dL. In addition, the percent of missed bolus doses per month and the average number of missed bolus doses per day will be estimated in subjects with T1D and T2D on both the blinded and unblinded CGM. The final secondary objective will estimate the average number of MSBD events per month in subjects with T1D or T2D using data obtained from the blinded and unblinded CGM phases of the study.

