9.3 Bolus Insulin Regimen and Dose Change

The data collected in the CRF Bolus Insulin Regimen at screening and CRF Bolus Insulin Dose Change at post screening visits will be summarized. The focus will be on the dose change (Yes or No). The detail of the bolus insulin regimen will be presented in the data listing(s).

[figure not shown]

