10.1 Missed Bolus Doses (MBD)

Missed bolus doses will be identified by using the CGM and Pen data.

2.

3.

4.

CCI

CCI

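### The missed-bolus endpoint counts only omissions followed by a CGM rise of at least 80 mg/dL, so differences by diabetes type or CGM period can arise without a difference in dosing behaviour

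*Protocol*

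**What the plan says.** Protocol 9.1.1 bases the primary endpoint on the CGM trace: "Missed bolus doses will be determined by the glucose excursion as measured by the CGM". A subject is counted as missing one injection if he or she "does not have any injection record during the 1-hour interval prior to a glucose excursion (≥ 80 mg/dL) in the 2-hour postprandial interval". Protocol 9.1.2 carries the rule into Study Period 2: "Missed bolus doses will be determined by the glucose excursion as measured by the unblinded CGM". SAP 10.1 agrees in outline ("Missed bolus doses will be identified by using the CGM and Pen data"), but its detailed algorithm is redacted.

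The results are meant to be compared. Protocol 3.1 says that "the study will explore any differences in missed bolus insulin doses by diabetes type, by CGM (blinded, unblinded), and by subject characteristics", and Protocol 5.4 gives possible differences by disease type as the reason for enrolling both populations. SAP Table 14.2.1 puts the blinded and unblinded periods in adjacent columns. Tables 14.2.3.6.1 and 14.2.3.6.2 report the two diabetes types separately.

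Three features of the design bear on how far glucose rises:
- **Continued therapy.** Protocol 7.1: "Subjects will continue their pre-study concomitant anti-hyperglycemic medication and basal insulin therapies during the study".
- **An exclusion for one type only.** Criterion [16] in Protocol 6.2 removes "Subjects with T1D who have taken off-label antihyperglycemic agents within 3 months prior to screening". There is no counterpart for type 2 diabetes.
- **What changes in Period 2.** Subjects and staff see the CGM data (Protocol 7.3). Insulin recommendations are made at Visit 4 (Protocol 5.1.3), the date on which the Period 2 analysis window opens (SAP 10).

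**The concern.** A skipped bolus followed by a rise of less than 80 mg/dL leaves no trace in the endpoint. What is counted is omission multiplied by the chance that an omission is detected, and that chance depends on physiology and background treatment as well as on behaviour.

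If the chance is the same in every group, the estimate is low but comparisons keep their meaning. If it differs between groups, a difference in days per month with a missed bolus can reflect glycaemic response alone. The study's question is dosing behaviour, so a reader of the type 1 and type 2 tables, or of the two period columns, could take a difference in detection for a difference in adherence.

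The pen could supply a check that does not depend on glucose. It records every injection. The prescribed regimen is taken at the start and later adjustments are documented for analysis (Protocol 5.5). No visible table brings the two together: Table 14.1.6 is a total of CGM and pen measures per subject (SAP 8.6), and SAP 9.3 tabulates dose change as yes or no and leaves regimen detail to listings.

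**Working it through.** **The plan's own figures.** The plan states no detection rate, standard deviation or effect size. Its one derived sample-size figure, 80 screened, reproduces as 68 / (1 − 0.15) = 80, but has no bearing here.

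**Inputs.** Three mealtime boluses a day, the minimum in Protocol 6.1. True 3.3 days per month, the only missed-day rate in the documents (Protocol 3.1; self-reported, among those who reported omission). The omission probability p = 0.15 and the detection probabilities s are assumptions.

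**Formula.** With omission probability p per meal, the same in every group, and a 30-day month:

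observed days = 30 × [1 − (1 − p·s)³]

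A true 3.3 days requires p = 1 − (1 − 3.3/30)^(1/3) = 0.0381. With p = 0.15 the true figure is 30 × (1 − 0.85³) = 11.58.

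| Detection s | True 3.3 days | True 11.58 days |
|---|---|---|
| 0.9 | 2.98 | 10.58 |
| 0.7 | 2.34 | 8.49 |
| 0.5 | 1.68 | 6.26 |
| Gap, 0.9 v 0.5 | 1.30 | 4.33 (unrounded inputs) |

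**Second parameterisation.** Let the rise after an omitted dose be normal with assumed SD 40 mg/dL, so that s = 1 − Φ((80 − μ)/40). Assumed means μ of 120, 100 and 80 mg/dL give s = 0.84, 0.69 and 0.50. With a 30.4-day month:

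| True days | s = 0.84 | s = 0.69 | s = 0.50 | Gap 0.84 v 0.69 | Gap 0.84 v 0.50 |
|---|---|---|---|---|---|
| 3.3 | 2.79 | 2.30 | 1.68 | 0.49 | 1.11 |
| 8 | 6.83 | 5.69 | 4.20 | 1.14 | 2.63 |
| 15 | 13.04 | 11.06 | 8.34 | 1.98 | 4.70 |

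A simulation of 21-day windows, with between-subject spread in omission (beta, concentration 6; 3,000 runs), gave somewhat smaller gaps at 0.84 v 0.50: 0.92 to 0.96, about 2.2 and about 4.0 days. With equal detection the mean difference was within 0.04 day of zero.

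**Which route applies in Period 2.** An excursion with an injection in the preceding hour is never counted. Smaller rises after boluses that were taken therefore leave the count unchanged; only the rise after an omitted dose matters. A changed mealtime dose cannot act at a meal where it is not injected. What remains is basal insulin, other agents, carry-over from earlier injections, and subjects responding to a rise they can now see.

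**Direction.** The arithmetic covers under-detection only. The rule can also over-count: a rise of 80 mg/dL with no omission, or a bolus injected after the nadir, is scored as missed.

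**The case against.** The study is exploratory and descriptive, states its detection rule openly and plans no formal test by type or period. That stands, and it makes this a matter of interpretation and not of error rates.

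A reader might infer that nothing planned could reveal the problem. The documents do not support that. Table 14.1.6 summarises pen measures within the analysis periods, treating records no more than 30 minutes apart as one injection, and SAP 6 sets periods side by side by default. Injection counts by period, independent of glucose, may therefore be available. Protocol 10.3.4 plans summaries of bolus dose and exposure, and Listing 16.2.8 holds the injection records. The percent of missed bolus doses needs a denominator, which could be prescribed doses; its rule may sit in the redacted part of SAP 10.1. What stands is narrower: no visible table sets injections against prescription or splits them by diabetes type.

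The mechanisms are also inferred. Continued therapy applies to all subjects, the exclusion concerns only off-label agents in type 1 diabetes, and Protocol 6.3 asks for stable diet and exercise. No excursion data by type or period are given. That limits the claim to what may happen.

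**Conclusion.** The point holds as a limit on interpretation. By its visible definition the endpoint counts detected omissions, and differences between types or periods can arise with identical dosing. Neither size nor direction can be established from the documents. Under assumed detection of 0.9 v 0.5 the spurious gap is about 1.3 days per month at the only cited rate and 4.3 at an assumed true 11.6. With a narrower contrast (0.84 v 0.69) it is about half a day at 3.3.

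Two stronger readings should be resisted. The 4.3-day gap is not an estimate of bias in this trial, since it rests on an assumed omission rate well above the cited one. Nor do Visit 4 insulin changes lower the count by flattening excursions in general, because excursions after an injected bolus are not counted at all.

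**What to change.** Keep the primary definition. For the same analysis windows, add supportive rows by period and by diabetes type (Tables 14.2.1, 14.2.3.6.1 and 14.2.3.6.2):

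1. Pen injections per day, using the 30-minute rule of SAP 8.6.
2. Days per month with fewer pen injections than the currently prescribed number of mealtime boluses, as far as the Bolus Insulin Regimen and Bolus Insulin Dose Change CRFs record that number. Their fields are not shown in the documents.

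In the report, describe differences in the excursion-based endpoint as differences in detected missed doses. Do not attribute them to dosing behaviour when the pen-only rows do not support it. Agreement between the measures is supportive and not proof: if subjects who see their glucose add correction injections, both measures could fall in Period 2 with no change in mealtime omission.

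The cost is SAP wording and a few table rows from data already collected. The downside is that the pen-only count reads high when meals are properly skipped, and low when correction or snack injections stand in for a missed mealtime dose. It is a cross-check and not a replacement.

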Subjects will be instructed to insert a new sensor weekly and recalibrate the CGM device throughout the study. At Visit 2 (Week 3) and Visit 3 (Week 6), subjects will have their blinded CGM data and pen data downloaded by the study site personnel.

5.1.3. Study Period 2

Following the completion of Visit 3 (Week 6) assessments, subjects will begin Study Period 2 and will be unblinded to their CGM data.

At Visit 4 (Week 9), subjects will have their unblinded CGM data and pen data downloaded by the study site personnel and any required adjustments to their CGM device alarms will be performed by the study site. Insulin adjustment recommendations will be provided by the investigator and designated staff based on the available glucose and insulin data. At Visit 5 (Week 12), subjects will complete their participation in the study, and the site will download all of the pen and CGM data since the last visit.

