9.2.1.1. Severe Hypoglycemia

Severe hypoglycemia is defined as an event accompanied by neuroglycopenic symptoms that result in cognitive impairment such that the patient requires assistance of another person to actively administer carbohydrate, glucagon, or perform other resuscitative actions. During these episodes, the patient has an altered mental status, and cannot assist in their care, is semiconscious or unconscious, or experienced coma with or without seizures, and may require parenteral therapy. Plasma glucose measurements may not be available during such an event, but neurological recovery attributable to the restoration of self-monitored blood glucose (SMBG) concentration to normal is considered sufficient evidence that the event was induced by a low SMBG concentration (≤ 70 mg/dL).

Documented symptomatic hypoglycemia is defined as an event that is accompanied by signs/symptoms of hypoglycemia, and is accompanied by a measured SMBG concentration of ≤ 70 mg/dL.

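### The protocol's missed-dose rule sets no floor on starting glucose, so a rise that follows low glucose can be scored as a missed mealtime bolus

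*Protocol*

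**What the plan says.** Protocol 9.1.1 is the only unredacted statement of how the primary endpoint is counted. It gives the data source: "Missed bolus doses will be determined by the glucose excursion as measured by the CGM". It then gives the rule: one missed injection is counted "if the subject does not have any injection record during the 1-hour interval prior to a glucose excursion", specified as a "glucose excursion (≥ 80 mg/dL) in the 2-hour postprandial interval".

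The worked example in the same section reads the excursions from nadir and peak times on a CGM trace: "2 glucose excursions ≥ 80 mg/dL within a 2-hour interval are observed". One of the two has no pen record in the hour before its nadir, "then the subject has 1 missed injection corresponding to the 11 am-12 pm glucose excursion". The text of the example gives neither a meal time nor a starting glucose.

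SAP 10.1 names CGM and pen data as the sources for identifying missed doses. Its numbered definitions are redacted. SAP 8.6 shows that they exist, because it refers to definitions 2 and 3 of that section, including the merging of pen records no more than 30 minutes apart.

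The primary endpoint (protocol 10.3.2.1) is days per month with a missed dose, taken from the last three weeks of the blinded period, scaled to a month and given with a 95% confidence interval.

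**The concern.** The word *postprandial* limits the rule to meals, but nothing in the listed data can apply that limit. In the Schedule of Activities (protocol Section 2, SAP 4.2) there is no record of meals, carbohydrate intake or treatment of lows. In practice the excursion itself stands in for the meal. With no condition on starting glucose, a recovery from a low looks the same to the rule as a meal eaten without insulin.

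The endpoint is a day-level indicator, so one such rise turns an otherwise clean day into a missed-dose day. The same event count feeds the percent of missed doses, the number per day, the subgroup tables and the missed-and-suboptimal-dose (MSBD) summary.

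The comparison of periods could also be affected. At Visit 4, which opens the Weeks 9-12 window, "any required adjustments to their CGM device alarms will be performed by the study site" and insulin recommendations are given (protocol 5.1.3). If either changes how often lows occur or how they are treated, a change in recovery rises could be read as a change in dosing behavior.

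**Working it through.** **1. Reproduce the worked example.** The 11 am to 12 pm rise has no injection from 10 to 11 am, so it is missed. The 1:30 to 2:15 pm rise has one injection from 12:30 to 1:30 pm, so it is covered. The total is 1, as the protocol states. Neither nadir value was needed to reach it.

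**2. Apply the numeric criteria to a recovery.** A rise from 60 to 150 mg/dL is 90, which is at least 80. Rises from 54 to 134 and from 70 to 150 are exactly 80. All of these end inside the plan's range of >70 to ≤180 mg/dL. With no bolus in the hour before the nadir, each counts as one missed injection.

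**3. Look for a record that could separate the two.** Protocol Appendix 2.2.1 mentions diaries only as generic examples of source documents. Hypoglycemia is recorded as an adverse event when the participant reports it (protocol 9.2; 9.2.1.1 begins one definition "Documented symptomatic hypoglycemia is defined as an event that is accompanied by signs/symptoms of hypoglycemia"). No visible text links those records to the missed-dose count.

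**4. Illustrate the size.** Assumptions: a month is 30.4 days, *T* is true missed-dose days per month, and *h* is the daily probability of a recovery rise that meets the rule, independent of true misses. Every true missed-dose day is taken as detected.

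Observed days = 30.4 × [1 − (1 − *T*/30.4)(1 − *h*)] = *T* + (30.4 − *T*) × *h*

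The documents give no value for *h*. The value *T* = 3.3 is the survey figure that protocol 3.1 cites for patients who omit insulin; *T* = 15 is an assumed high rate.

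| Assumed rate of recovery rises | *h* | *T* = 3.3 | *T* = 15 |
|---|---|---|---|
| One per month | 1/30.4 | 3.3 + 27.1/30.4 = 4.2 | 15 + 15.4/30.4 = 15.5 |
| One per 2 weeks | 1/14 | 3.3 + 27.1/14 = 5.2 | 15 + 15.4/14 = 16.1 |
| One per week | 1/7 | 3.3 + 27.1/7 = 7.2 | 15 + 15.4/7 = 17.2 |

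The relative increase is 27% to 117% at 3.3 days, and about 3% to 15% at 15 days. The formula already allows for recovery rises that fall on a day with a true miss.

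**5. Compare with the confidence interval.** With 50 completers the half-width is t(0.975, 49) × SD/√50. The plan states no SD. For an assumed SD of 2, 4, 6 or 8 days the half-width is 0.6, 1.1, 1.7 or 2.3 days. At *T* = 3.3 the weekly case (+3.9) exceeds all four, and the monthly case (+0.9) exceeds only the first. The interval describes sampling error and would not reflect this bias.

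**6. Allow for under-counting.** If a fraction *s* of true missed-dose days is detected, with *p* = *T*/30.4, the two errors cancel when *h* = *p*(1 − *s*)/(1 − *sp*).

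- *T* = 3.3 (*p* = 0.109): *s* = 0.5 gives *h* = 0.057, or 0.4 per week; *s* = 0.9 gives 0.012, or 0.08 per week.
- *T* = 15 (*p* = 0.493): *s* = 0.5 gives about 2.3 per week; *s* = 0.9 gives about 0.6 per week.

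Cancellation is possible, but only at particular rates.

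**The case against.** The strongest reply is that the algorithm that will actually be run is in SAP 10.1 and is redacted. SAP 8.6 shows that it refines the protocol rule, and it may already hold a glucose floor. That stands. The finding is about the protocol text, and nothing can be said about whether the SAP lacks an exclusion.

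A second reply is that the rule is confined to the post-meal interval and does not take in every rise. That is correct as wording. It does not settle the point, because the named sources are CGM and pen only and neither records a meal.

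Third, a reader might infer that the primary estimate is inflated, by 27% to 117%. The documents do not support that. An omitted dose followed by a rise below 80 mg/dL is not counted, and any injection in the prior hour counts as cover, so the net direction is unknown. The percentages rest on an assumed frequency and on one self-reported baseline. That baseline covers insulin omission in general among the one-third who omit. It is not an expected rate of missed mealtime doses in a population entered with HbA1c of at least 8.0%.

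Fourth, a reader might infer that the blinded-versus-unblinded comparison is distorted. The documents give no frequency of lows in either period. The primary endpoint uses blinded data only, and the comparison is exploratory and descriptive. A difference between periods is possible but not shown.

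Finally, a nadir cut at 70 mg/dL is imperfect: it keeps recoveries from just above 70 and other non-meal rises. This is a reason to show results both ways and not to replace the main count.

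**Conclusion.** The point holds for the rule as the protocol states it. Rises after low glucose can be scored as missed mealtime boluses, because there is no starting-glucose floor and no listed record to enforce the post-meal limit. Considered alone, this error works in one direction only, toward more missed-dose days. How large it is, and whether it outweighs the under-counting, cannot be determined from the documents; the figures in the table hold only under the stated rates, independence and full detection. An opposing error of unknown size does not validate the count, and nothing ensures that the two balance, or balance equally in both periods. In a descriptive study whose main product is this one estimate, a low-cost check is proportionate.

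**What to change.** First establish whether the definitions in SAP 10.1 already exclude excursions that start from low glucose. If they do, bring protocol 9.1.1 into line with them.

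If they do not, keep the count as defined and add a paired display: the primary endpoint, and the missed-dose and MSBD summaries for both periods, with and without excursions whose nadir is at or below 70 mg/dL. That value is the lower bound of the plan's own glucose range. State the nadir condition in protocol 9.1.1 and SAP 10.1, and carry it into SAP 10.3.

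The cost is a few lines of text and code on CGM data already collected. The downside is that the version with the exclusion loses truly omitted meal doses that begin from a low nadir. The gap between the two versions shows how many events are in question.
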